Research has shown that a successful implementation depends on interplay between the effectiveness of the implementation strategies chosen to support the implementation and characteristics of the implementation object, the implementers, the target population and the context of the implementation (Table 1).

Updated design of the implementation research

The project was planned to be conducted using a cross-over design in two counties in south of Sweden based on a feasibility/pilot study that was conducted during fall 2014 *co-created palliative care educational intervention through seminars for professionals in nursing homes*. Due to a more significant amount of drop-outs compared with expected (and for not receiving the total amount of applied foundation), the plan needed to be revised. The knowledge-based palliative care intervention was conducted as a non-randomized control trial, implemented over a six-month period in 30 nursing homes in two different counties in the south of Sweden (County A and County B). The data collection was made in two sequential periods in each county. First, the intervention was implemented in ten nursing homes in County A (Kronoberg County from April 2015), while ten nursing homes in County B served as a control group. Then, County B implemented the intervention (Skåne county from August 2016), and ten new nursing homes in County A, which had not received the intervention, were chosen as a control group. After the two sequential time periods were data from one intervention and one control group analysed. The selection through voluntary participation resulted in a mixture of both larger and smaller nursing homes within the two counties (cluster samples), as well as both from urban and rural areas.

Implementation object

According to the National Board of Health and Welfare, palliative care should be based on four cornerstones: symptoms relief, multi-professional cooperation, communication and relation as well as support to the next of kin (Socialstyrelsen 2012). The aim of palliative care is to reduce suffering and promote the quality of life for patients with progressive, incurable illnesses or injuries. The care should address physical, psychosocial and spiritual needs as well as provide support to the next of kin. The definition by the National Board of Health and Welfare closely

adheres to the definition of palliative care by the World Health Organization (WHO), (Socialstyrelsen 2013).

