The evaluation consist of 8 studies and involves four implementation outcomes in accordance with the framework proposed by Proctor *et al.* (2011): **Acceptability** - The perception among implementers (nursing home staff and managers) that a given knowledge-based practice (palliative care in nursing homes) is agreeable, towards benefit or satisfactory; **Appropriateness** - The perceived fit, relevance or compatibility of an knowledge-based practice (palliative care), for a given practice setting, provider, or consumer (older persons and their next of kin); **Feasibility** - The extent to which an knowledge-based practice (palliative care) can be successfully used or carried out within a given agency or setting (nursing homes); and **Fidelity** - The degree to which an knowledge-based practice (palliative care in nursing homes) was implemented as it was prescribed in the original protocol (the knowledge documents concerning palliative care).

Participants in studies

The persons asked for participation in this study, i.e. older persons, next of kin, staff and leaders are recruited from the included nursing homes in both Skåne and Kronoberg counties. The persons are selected consecutively until the stipulated figures are reached (Table 2).

Methods and instruments

The following methods and instruments will be used in this project:

Questionnaires

Quality of life: The WHOQOL-BREF questionnaire (WHO, Manual 1996) and the WHOQOL-OLD questionnaire (WHO, Manual 2006) assessed quality of life. The older persons and next of kin will answer to the questions in a structured interview. The WHOQOL-BREF is often used together with the WHOQOL-OLD module and both are psychometric tested by the WHOQOL Group (Power *et al.*, 1999). The WHOQOL-OLD module have been validated for old people in several countries, for example Sweden (Power *et al.* 2005) and can be used in a wide variety of studies including cross cultural investigations, population epidemiology, health monitoring, service development, and clinical intervention trials in which issues about quality of life are crucial (WHO, Manual 2006). The project has acquired permissions from WHO to use these questionnaires and in order to make it easier to answer the questionnaires, the answer alternatives will be enlarged on a separate paper and used during the interview.

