Official title of the study:
Implementation of Knowledge-Based Palliative
Care for Frail Older Persons in Nursing Homes

NCT number: NCT02708498

Date of the document: April 8, 2015, updated October 6, 2020

Statistical Analysis Plan

Simple descriptive statistics:

Median-Mean, Quartiles, Percentage

These are applied to all quantitative studies.

Baseline study:

Target population: Older people

Instruments: Characteristics of older participants, WHOQOL-BREF & WHOQOL-OLD

The data were analysed in one descriptive and one analytical section. In the descriptive section, numbers and percentages were calculated on a group level. A mean score was calculated for each domain using both the raw domain score, a standardized domain score (SDS) with the raw domain score divided by the number of items in the domain (1-5) and a transformed domain mean score (TDS 0-100) according to the instrument manuals. The different calculations were performed to enable comparison of our results with those from other studies.

In the analytical section, the participants were divided into two age groups (66-88 years and 89-102 years) by the population median age and gender (female and male). To examine differences in quality of life, a comparison of medians was conducted using the Mann-Whitney U test.

Comparative studies (Baseline and Follow-up):

Target population: Older people, next-of-kin, staff

Instruments: PCAT, PCQ-S, PCQ-P, WHOQOL-BREF, WHOQOL-OLD, Your experience of palliative care, Next-of-Kin Participation in Care (NoK-PIC)

The selection of the statistical tests to analyze data other than the descriptive statistics was based on whether the data were distributed normally and the scale level of the instruments. The Mann-Whitney U-test and the Kruskal-Wallis test was applied to compare the baseline characteristics of the two groups. The quantitative data collected from questionnaires were analyzed using within-group comparisons (the data from after the intervention period were compared with the data from before the intervention period in the intervention group and the control group) by Wilcoxon signed rank test.

Either Pearson's chi-square test or Fisher's exact test was used when the expected value was less than 5.

A two-tailed p-value of <0.05 was regarded as statistically significant.

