In order to investigate if the drop-outs consisted a threaten of external validity we performed sub-groups analysis through comparing the drop-outs in the intervention group with the participants in the intervention group, and comparing the drop-outs within the control group with the participants in the control group.

Analyses were performed using IBM SPSS Statistics version 24.

Logistic regression studies (Baseline and Follow-up):

Target population: Staff
Instruments: P-CAT, PCQ-S

A univariate logistic regression analysis was performed with the independent variable improvement/non-improvement in P-CAT and PCQ-S and the dependent variable group (control/implementation).

Psychometric studies

Target population: Next-of-kin
Instrument: Next-of-Kin Participation in Care (NoK-PiC)

Step 1. Dimensionality

The dimensionality of the 37 items was explored by means of Rasch Model Analysis (RMA) and Explorative Factor Analysis (EFA). EFA needs complete data, i.e. no missing responses in any items. RMA can process missing data. Estimation methods merely summarize the non-missing observations that are relevant, and compare them with their expectations.

NoK-PiC data was analysed according to Rasch Measurement Theory (RMT), using the polythomous Rasch model in RUMM2030 (Professional Edition 5.4). A principal component analysis of the residuals was conducted in RUMM2030 to explore dimensionality of the NoK-PiC items. Person location estimates were derived from subsets of items that loaded positively and negatively on the first principal component of residuals. The overall proportion of persons with significantly different measures from the two item subsets should be <5% to support unidimensionality.

EFA was conducted based on recommendations including parallel analysis to decide for decision about how many factors to retain for rotation, Minimum Rank Factor Analysis (MRFA, that is able to estimate the percentage of common variance explained by the EFA model), and on a promine rotation that allows factors to correlate (oblique). In addition, since the items are polythomous, and since MRFA assume only minor departures from normality, we based the analysis on a polychoric correlation matrix. The software FACTOR (Lorenzo-Seva, Ferrando, release 10.5.03, June 2017) was used to conduct EFA.

Step 2. Item reduction

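### Non-randomised arms are compared without adjustment for baseline score, person or home characteristics, and the baseline tests used to judge comparability lead to no action

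*SAP*

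**What the plan says.** The protocol (Updated design of the implementation research) states that "The knowledge-based palliative care intervention was conducted as a non-randomized control trial". On how homes entered, it says "The selection through voluntary participation resulted in a mixture of both larger and smaller nursing homes within the two counties (cluster samples", and adds that urban and rural areas are both represented. Each county supplies homes to both arms in different periods; in the second period "ten new nursing homes in County A, which had not received the intervention, were chosen as a control group". Within homes, "The persons are selected consecutively until the stipulated figures are reached (Table 2".

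The SAP (Comparative studies) says: "The Mann-Whitney U-test and the Kruskal-Wallis test was applied to compare the baseline characteristics of the two groups". It does not say what follows if a test is significant, or what is concluded if it is not. On outcomes: "The quantitative data collected from questionnaires were analyzed using within-group comparisons", by Wilcoxon signed rank test in each arm. Chi-square and Fisher tests are named without a stated purpose. Drop-outs are compared with participants inside each arm, which does not bear on comparability between arms.

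The one model that links arm to outcome is in the SAP's logistic regression section and covers staff only: "A univariate logistic regression analysis was performed with the independent variable improvement/non-improvement in P-CAT and PCQ-S and the dependent variable group (control/implementation". Of the descriptive statistics (means, medians, quartiles, percentages) the SAP says "These are applied to all quantitative studies".

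**The concern.** Without randomisation, and with homes that chose to take part, nothing in the design balances the people or homes in the two arms apart from the partial balance of county. Any further protection against measured confounding has to come from the analysis, and the SAP offers a significance test in its place. A non-significant test in a small sample does not show that arms are alike, and a significant one changes nothing in what is done next.

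The documents themselves treat the omitted variables as relevant. The SAP's baseline study compares quality of life by age group and gender. The protocol's Significance section raises urban/rural differences in palliative care quality as an open question, and its theoretical framework names context as a determinant of implementation. None of these enters an arm comparison. The overall aim is to evaluate outcomes and effectiveness, so what is at stake is whether a difference in improvement between arms can be credited to the intervention or partly reflects who was in each arm at the start.

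**Working it through.** **1. Search for an adjusted arm comparison.** The SAP's analyses are: rank tests of baseline characteristics, paired tests within each arm, chi-square/Fisher tests, drop-out comparisons within arm, one univariate staff regression, and psychometric work. There is no ANCOVA, multivariable model, matching, weighting or stratified arm comparison. Age and gender appear only in the baseline quality-of-life comparison and in the check for differential item functioning. Home size and setting appear in no analysis.

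**2. Inputs.** Table 2 gives 20 older persons, 100 next of kin (sub study 3) and 100 staff, read here as totals per arm. The SAP gives two-sided 0.05. The documents state no SD, effect size, power or correlation, so there is no planned figure to reproduce. Assumed: imbalance *d* = 0.3 or 0.5 SD, baseline to follow-up correlation *r* = 0.5 to 0.7, normal scores, independent persons, and improvement meaning follow-up above baseline (the SAP does not define it).

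**3. Power of the baseline test.** With the Mann-Whitney efficiency of 0.955 under normality, power ≈ Φ(*d*·√(0.955*n*/2) − 1.96), plus a negligible opposite tail.

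| n per arm | d | d·√(0.955n/2) | Power |
|---|---|---|---|
| 20 | 0.3 | 0.927 | 15% |
| 20 | 0.5 | 1.545 | 34% |
| 100 | 0.3 | 2.073 | 55% |
| 100 | 0.5 | 3.455 | 93% |

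The imbalance found with 80% power is 2.80·√(2/(0.955*n*)): 0.91 SD at 20 per arm and 0.41 SD at 100. If Table 2 is instead per county, so 40 and 200 per arm, power for 0.3 SD is Φ(1.311 − 1.96) = 26% and Φ(2.932 − 1.96) = 83%.

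**4. No true effect, imbalance regresses to a common mean.** Let the intervention arm start *d* lower, with follow-up = *r*·baseline + error of variance 1 − *r*² in both arms. Mean change is then (1 − *r*)*d* in the intervention arm and 0 in control, with SD √(2(1 − *r*)). The chance of improvement is 0.5 in control and *p* = Φ(*d*·√((1 − *r*)/2)) in the intervention arm, so OR = *p*/(1 − *p*). The rejection rate at 100 per arm uses *z* = (*p* − 0.5)/√(0.25/100 + *p*(1 − *p*)/100).

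| d | r | p | OR | False positives (formula) | Simulated, 4,000 runs |
|---|---|---|---|---|---|
| 0.3 | 0.7 | 0.546 | 1.20 | 10% | 10% |
| 0.3 | 0.5 | 0.560 | 1.27 | 14% | 16% |
| 0.5 | 0.7 | 0.577 | 1.36 | 19% | 21% |
| 0.5 | 0.5 | 0.599 | 1.49 | 29% | 31% |

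If the intervention arm starts higher, the odds ratios invert (0.83 to 0.67) and a real benefit can be hidden.

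**5. No true effect, stable difference.** If the intervention arm is *d* lower at both visits, change has the same distribution in both arms. The OR is 1 and the simulated false-positive rate is 5 to 6%. Adjusting for baseline score now introduces a bias of size (1 − *r*)*d*, with SE ≈ √(2(1 − *r*²)(1 + *d*²/4)/100).

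| d | r | Bias/SE | False positives, baseline-adjusted |
|---|---|---|---|
| 0.3 | 0.7 | 0.09/0.102 | 14% |
| 0.3 | 0.5 | 0.15/0.124 | 23% |
| 0.5 | 0.7 | 0.15/0.104 | 30% |
| 0.5 | 0.5 | 0.25/0.126 | 51% |

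**6. How the two analyses relate.** The change-score estimate is the follow-up difference minus the baseline difference. The baseline-adjusted estimate subtracts only *b* times the baseline difference, where *b* is the pooled within-arm slope. They differ by (1 − *b*) times the observed baseline difference. A small observed difference makes them agree; a large one makes the choice matter.

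**The case against.** Several points on the other side stand.

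- A reader might infer that case-mix differences pass straight into the arm effect. They do not: the paired tests and the improvement variable both use within-person change, so a stable level difference cancels (step 5). What remains is regression to the mean, ceiling effects and trends that vary with case mix.
- A reader might infer that naming group as the dependent variable causes bias or rules out adjustment. With one binary predictor, the odds ratio and its test are the same in either direction. The conditional odds ratio is also essentially symmetric: a simulated check with two confounders gave log odds ratios of 0.685 and 0.684. The reversal may be only a slip of labelling.
- A reader might infer that the arms are known to differ in home size or setting. The protocol reports a mixture within the counties, not a difference between arms, and the county swap gives partial balance on county.
- For older persons and next of kin the SAP names no between-arm outcome test, so no stated arm effect exists there to be biased. That gap is a different defect.
- The baseline test is not always weak. At 100 per arm it flags 0.5 SD 93% of the time. In a null simulation at that size, a false positive together with a missed imbalance occurred in under 1% of trials at 0.5 SD and about 3% at 0.3 SD. Descriptive statistics would also let a reader see the size of an imbalance.

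The last point does not rescue the plan. Detecting or seeing an imbalance corrects nothing when no analysis responds to it.

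**Conclusion.** The point holds in a limited form. Volunteer, non-randomised arms are judged comparable by tests with no stated consequence. Those tests have low power for a 0.3 SD imbalance at 20 per arm (15%) and moderate power at 100 (55%). No arm comparison adjusts for anything.

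The possible harm depends on how an imbalance behaves. Under regression to a common mean, with 0.3 to 0.5 SD and *r* of 0.5 to 0.7, the staff analysis at 100 per arm would show an odds ratio of about 1.2 to 1.5 with no true effect, and false positives of about 10 to 31% instead of 5%. Under a stable difference there is no bias in the unadjusted change analysis. The documents do not say which applies, and neither the imbalance nor the correlation is given. The figures therefore show what could happen; they do not estimate what did happen. They also ignore clustering within homes, county and period, which are separate matters.

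**What to change.** - Replace the baseline significance tests with a table of standardised differences between arms for baseline scores, person characteristics and home characteristics.
- For each outcome, specify one between-arm model with follow-up score (or change) as the response and arm as the predictor. Adjust, whatever the baseline p-values, for baseline score and a short fixed list of recorded covariates: age, gender, and home size and urban/rural setting where available. With 20 per arm, keep to baseline score plus one or two.
- Report alongside it, as sensitivity analyses, the covariate-adjusted change-score analysis without baseline score and the unadjusted result. Baseline-score adjustment must not stand alone, because it is biased by (1 − *r*)*d* if the arm difference is stable.
- State in advance that the conclusion rests on agreement between these analyses, and that disagreement will be reported as uncertainty about confounding.

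The cost is SAP wording and a re-run, a few degrees of freedom, and the possibility that the analyses disagree. No new outcome data are needed. The documents do not confirm that home size, setting, or staff age and gender were recorded as analysis variables, so that has to be checked before the covariate list is fixed.

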Sub study 5: Staff	Focus group interviews (preparedness for implementation)	20 staff divided into 3 groups before and after the implementation is finished	
Sub study 6: Staff	Questionnaires at two occasions: Experiences of palliative care (46 items), P-CAT (13 items) and the Person-Centered Climate Questionnaire (14 items)	100 staff before and after the implementation is finished	100 staff with 6 months in between
Sub study 7: Managers	Two individual interviews with managers (organic preparedness for implementation)	20 managers at different levels-, during the intervention and after six months	
Sub study 8: Implementation context	An ethnographic study: Observations and qualitative interviews	Observations on 28 occasions at 7 nursing homes with a strategic selection of qualitative interviews during the implementation	

THE OVERALL AND SPECIFIC AIMS

The overall aim of this research project is to evaluate the outcomes and effectiveness of the implementation method of a knowledge-based model for palliative care in nursing homes. The overall aim can be broken down into four specific research questions and nine different studies:

1. What is the outcome of the implementation intervention in terms of quality of life, participation and quality of care in older persons and next of kin at nursing homes before and after? (Study I, II-IV)
2. Investigates the staff's implementation process of palliative care and the role of the leadership and (Study V-IX).
3. Investigate which factors (barriers and facilitators) that affect the implementation process of this model (Study V, VII-IX).

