Based on conceptual reasoning among the researchers and based on RMA item reduction was conducted. The main statistical reasons for item reduction was based on item fit. In general, individual item fit residuals should range between -2.5 and 2.5, with the ideal being 0. Signs of multidimensionality/under discriminating items (fit residuals >2.5) and local dependency/item redundancy/over discriminating items (fit residuals > -2.5) led to further exploration of the possible reasons for misfit. This exploration included inspection of item residual correlations, and the item characteristic curves to get a graphical understanding of the deviations from Rasch model expectations. The nature of observed misfit (local response dependence or multidimensionality) often needs to be determined based on conceptual reasoning rather than statistics.

Step 3. Dimensionality after item reduction

Dimensionality of the remaining 30 items (after step 2) was explored using EFA, following the same procedures as described above (Step 1). The appropriateness of performing EFA was, in this step, checked according to quality criteria, i.e. by means of: the Kaiser-Meyer-Olkin Measure of Sampling Adequacy (should be KMO 0.50 or above); and Bartlett's test (should be p-value <0.05).

Step 4. RMA of final and separate factors

According to RMA, a set of items, supposed to be unidimensional, rated (dichotomous or polytomous scoring) in a sample, are compared to the "Perfect Rasch Model" that is based on fundamental measurement principles from the physical sciences. The model separately locates persons and items on a common interval level logit metric, ranging from minus to plus infinity, with mean location set at zero. The extent to which a successful measurement has been achieved is determined by examining the fit between observed data and model expectations. If data accord sufficiently with the model, linear measurement and invariant comparisons are possible. However, almost no scale is perfect, thus "almost perfect" can be a goal to achieve. Here the RMA addresses targeting, reliability, model fit, Differential Item Functioning (DIF, by gender and age), and hierarchical item ordering.

Step 5. Group comparisons

The IBM SPSS Statistics 23 software was used for comparisons between independent groups. Data were assessed regarding underpinning assumptions, described, and analysed using Mann Whitney U-tests. Significance was set to $P < 0.05$.

Target population: Next-of-kin

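### Eight of ten questionnaire outcomes, including every scale in older persons and next of kin, are tested only within each arm; no between-arm comparison of change is specified

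*SAP*

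**What the plan says.** The protocol, under the updated design, states: "The knowledge-based palliative care intervention was conducted as a non-randomized control trial". Ten County A homes received the intervention first, with ten County B homes as controls. County B then received it, with ten new County A homes as controls. The same section adds: "After the two sequential time periods were data from one intervention and one control group analysed". It does not say how the two were compared.

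Under the overall and specific aims, the protocol says: "The overall aim of this research project is to evaluate the outcomes and effectiveness of the implementation method". Research question 1 asks for the "outcome of the implementation intervention in terms of quality of life, participation and quality of care in older persons and next of kin".

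The SAP, under Comparative studies (Baseline and Follow-up), covers older people, next of kin and staff. On change it says: "The quantitative data collected from questionnaires were analyzed using within-group comparisons", by Wilcoxon signed-rank test in each group. On comparing groups it says: "The Mann-Whitney U-test and the Kruskal-Wallis test was applied to compare the baseline characteristics of the two groups". Under Logistic regression studies, for staff only: "A univariate logistic regression analysis was performed with the independent variable improvement/non-improvement in P-CAT and PCQ-S", with group as the other variable. In the psychometric study of NoK-PiC, Step 5 says that SPSS "software was used for comparisons between independent groups", without naming the groups.

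**The concern.** A before/after test within one arm asks whether that arm changed. It does not ask whether the intervention arm changed more than the control arm, which is what a control group is for. Followed as written, the within-arm tests give no effect estimate and no confidence interval for the arm difference. Change common to both arms (ageing of the sample, season, repeated questioning) would be visible but not subtracted.

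The likely misreading is to take a significant result in the intervention arm and a non-significant one in the control arm as evidence of an effect. That pattern does not show that the arms differ. The gap falls on the populations of research question 1, so the study's central controlled question would go unanswered for them.

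**Working it through.** **1. Count of outcomes.** From protocol Table 2 (sub studies 1, 3 and 6) and the SAP instrument list:

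| Population | Scales | Number | Between-arm analysis of change specified |
|---|---|---|---|
| Older persons | WHOQOL-BREF, WHOQOL-OLD, P-CAT, PCQ-P | 4 | 0 |
| Next of kin | NoK-PiC, WHOQOL-BREF, WHOQOL-OLD | 3 | 0 |
| Staff | Experience of palliative care, P-CAT, PCQ-S | 3 | 2 |

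Total 4 + 3 + 3 = 10; uncovered 10 − 2 = 8. Counting sub study 2 separately adds two WHOQOL scales and gives 10 of 12. The staff regression dichotomises change and is unadjusted. It names group as the dependent variable, but with one binary predictor the odds ratio is the same in either direction, so it counts as an arm comparison.

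**2. Other text that might supply the contrast.**
- Choosing tests by distribution and scale level selects a test, not a contrast.
- The chi-square/Fisher sentence names no variable, time point or groups.
- The WHOQOL Mann-Whitney test is a baseline comparison by age group and gender.
- The drop-out comparisons are made within each arm.
- NoK-PiC Step 5 mentions neither arms nor change.

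**3. Illustration of the misreading.** The documents state no expected change, SD or power, so there is no planned figure to reproduce. Assume normal, independent change scores, the same true change d (in SDs of individual change) in both arms, and two-sided 5% tests. With p the chance of a significant favourable result in one arm and w the chance of any significant result, the chance of favourable significance in the intervention arm only is p(1 − w). When p ≈ w this cannot exceed 0.5 × 0.5 = 0.25. Normal approximation at n = 100, d = 0.2: d√n = 2.0, p = w = 0.516, and 0.516 × 0.484 = 0.25.

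Simulated Wilcoxon signed-rank tests (20,000 replicates per case) give these favourable rates:

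| n per arm | d = 0 | 0.1 | 0.2 | 0.3 | 0.4 |
|---|---|---|---|---|---|
| 20 | 2.5% | 5.8% | 10.9% | 17.9% | 23.2% |
| 60 | 2.2% | 9.6% | 21.2% | 23.9% | 13.1% |
| 100 | 2.3% | 13.2% | 25.0% | 14.1% | 2.6% |
| 200 | 2.5% | 20.2% | 16.5% | 1.5% | 0.0% |

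A Mann-Whitney test of change between arms stays at 2.3% to 2.7% in the favourable direction throughout. Table 2 gives 20 and 100. The rows for 60 and 200 are assumptions, because the table does not say whether its figures are per arm, county or period, and the protocol reports more drop-out than expected. Sample size moves the peak but not its height.

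**4. Precision of the missing estimate.** The 95% CI half-width, in SDs of change, is t × √(2/n):
- n = 20: 2.024 × 0.316 = 0.64
- n = 60: 1.980 × 0.183 = 0.36
- n = 100: 1.972 × 0.141 = 0.28

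With an assumed ICC of 0.05 and 5 people per home and period (n = 100), the variance of the difference is 0.0215 if a County B home keeps the same effect in both periods, and 0.024 if it does not. The half-widths are 0.29 and 0.31.

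**5. What the arm difference contains.** Let A1, A2, B1 and B2 be the mean changes by county and period; A1 and B2 are intervention. With additive group, period and county effects, the group estimate is [(A1 − A2) + (B2 − B1)]/2. If a county-by-period effect c enters B2, this equals g + c/2, where g is the true group effect. Half of c therefore enters the arm difference.

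**The case against.** The SAP applies means, medians and quartiles to all quantitative studies. Reported by arm and time, these would let a reader form a crude difference in change. Chi-square/Fisher and NoK-PiC Step 5 are ambiguous, so an arm comparison may have been run. This is why the claim is that none is specified, not that none was done. A crude difference still has no uncertainty attached.

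The 25% figure depends on a decision rule that the SAP does not state. That is correct: it is an illustration, and the supported size is the count of 8 of 10.

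The SAP is written in the past tense and already contains results, so a new analysis cannot be pre-specified. That stands and must be declared.

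That the same County B homes served in both arms is inferred from 10 + 10 + 10 = 30. The protocol's ethical considerations mention only two control-only homes, which conflicts with ten new County A control homes. If homes are shared, some people may also appear in both arms, and the documents are silent on this. These points affect the model, not the need for the contrast.

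Finally, homes volunteered and were not randomised, so an arm difference cannot establish effectiveness alone. That limits what it proves, but is no reason to omit it.

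**Conclusion.** The concern holds and must be fixed. For 8 of 10 scale-by-population outcomes the SAP specifies within-arm tests and no between-arm analysis of change. Seven of the 8 are all the scales in older persons and next of kin; the eighth is the staff questionnaire on experience of palliative care. The count rests only on Table 2 and the SAP text. The false-inference rates (about 2.2% to 25%) are illustrative and assume a common true change, normal independent change scores and an unstated reading rule. The interval widths assume unit SD and, where clustering is included, an ICC of 0.05.

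**What to change.** For these 8 outcomes, and preferably all 10:

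- Make the main analysis a between-arm comparison of change or of baseline-adjusted follow-up. Fix which is primary before re-running, report the other as sensitivity, and give the arm difference with a 95% CI.
- One suitable form is a linear mixed model with group, period and county as fixed effects, baseline score as covariate in the adjusted version, and a nursing-home random effect spanning both arms where homes are shared. A rank-based comparison of change is closer to the SAP's current approach. If it ignores home, however, its two-sided error at 100 per arm with an ICC of 0.05 was 5.7% (home effect shared across periods) to 7.1% (not shared) in simulation.
- Name a fallback without a home effect for older persons. With 20 per arm over 20 homes there may be about one person per home and period. In simulation the home variance was then estimated as zero in 46% of runs at ICC 0.05 and 39% at ICC 0.10, against 20% and 5% with five people per home and period.
- Reconcile the number of control-only homes and state whether any home or person contributes to both arms.
- Say how multiplicity is handled. WHOQOL is scored by domain, so 8 outcomes means more than 8 tests.
- Keep the Wilcoxon tests as descriptive. Label the re-analysis post hoc, and state that homes were volunteers, not randomised, and that half of any county-by-period effect enters the arm difference.

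The cost is SAP wording and moderate re-analysis of data already collected. Estimates will be imprecise, and some significant within-arm results may no longer support a claim of effect.
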